#### **11. INFORMED CONSENT PROCESS**

---

It is the responsibility of the Investigator to inform each subject, prior to performing any study-related assessments, of the purpose of this clinical trial, including possible risks and benefits and document the informed consent process in the subject's chart. A sample informed consent form containing the required elements of informed consent is provided in [Appendix 2](#). Any changes made to this sample must be approved by the Sponsor or its designee, prior to submission to the IRB. After approval by the Sponsor or its designee, the informed consent must be submitted to and approved by the IRB. Prior to entry into the study or initiation of any study-related procedures, the subject must read, sign and date the informed consent form. The person executing the consent must also sign and date the final consent form page. The original informed consent form is to be retained by the study site and a copy is to be given to the subject.

The informed consent must be written in a language in which the subject is fluent. If a foreign language translation is required, a statement of certification of the translation must be issued. Regulations require that foreign language informed consent forms be submitted to the IRB for approval. The Investigator must forward a copy of the consent form, the certified foreign language translation and an IRB approval letter to the Sponsor or its designee.

---

---

## 12. CONFIDENTIALITY

---

In accordance with GCP and with the national data protection laws, all information concerning the subjects in the study must be treated as strictly confidential by all persons involved in the study.

The Investigator acknowledges that any and all information acquired from the Sponsor or its designee or developed or acquired in connection with the study are strictly confidential. The Investigator will not disclose any confidential information to any third party nor use confidential information for any purpose without first obtaining the consent of Sponsor in writing. Such consent shall be deemed to have been given for disclosure to any person for whom the Investigator is responsible at his/her center, but only so far as required for the purposes of the study, and, in the case of disclosures to staff, only if such staff are bound by obligations of confidentiality no less strict than those set out herein.

---

## 13. PROTOCOL AMENDMENTS

---

The Sponsor will document modifications to the protocol in the form of a written amendment. Protocol modifications that impact subject safety or the validity of the study must be approved by the IRB before implementation. In the case of a medical emergency, to remove immediate apparent hazard to subjects, a change may be made preferably after discussion with the Sponsor or its designee. In these instances, the IRB and FDA will be notified as soon as possible.

---

## 14. DATA MANAGEMENT

---

All data relating to study procedures will be entered into CRFs provided by the Sponsor or its designee. All requested information must be entered on the CRF. If an item is not available or not applicable this fact should be indicated.

Obvious errors (self-evident corrections) will be corrected and documented by the Sponsor or its designee. Other errors or omissions will result in queries which will be sent to the investigational site on Data Clarification Forms (DCF)/Query Forms for resolution. A copy of the signed DCF is to be kept by the site with the CRFs. Once the original is received by the Sponsor or its designee, the resolutions will be reviewed and entered into the database.

Data will be entered into a computer database developed specifically for this trial. Access to the database will be restricted to personnel responsible for data entry and to data management and statistics personnel who are directly involved in the management or analysis of this trial. During the course of the trial, data queries will be generated for data items that are potentially erroneous and require appropriate clarification or correction.

---

Prior to database lock, statistical verification of the data will be undertaken in order to further assure data quality.

---

## **15. RECORD KEEPING AND RETENTION**

---

Data generated for the study should be stored in a limited-access file area and be accessible only to representatives of the study site, the Sponsor and its representatives and FDA/relevant health authorities/regulatory agencies. All reports and communications relating to study subjects will identify subjects only by initials and subject identification number. Complete subject identification will be kept by the Investigator. This information will be treated with strict adherence to professional standards of confidentiality.

An Investigator must in reasonable time, upon request from any properly authorized officer or employee of FDA/relevant health authority or regulatory agency, permit such officer or employee to have access to requested records and reports, and copy and verify any records or reports made by the Investigator. Upon notification of a visit by the FDA/relevant health authority or regulatory agency, the Investigator will contact the Sponsor or its designee immediately. The Investigator will also grant Sponsor representatives the same privileges offered to FDA/relevant health authority or regulatory agents/officers/employees.

The Investigator must provide the Sponsor or its designee with the following documents prior to study initiation and retain a copy in the study file:

- A completed and signed Form FDA 1572. If during the course of the study any changes occur that are not reflected on the 1572, a new 1572 form must be completed and sent to Sponsor/CRO.
- Current signed curriculum vitae (within 2 years) and current medical licenses for the Principal Investigator and all co-Investigators listed on the 1572.
- A copy of the original approval for conducting the study by the IRB. Renewals, with continuance of the study, must be submitted at yearly intervals or as required by IRB policy.
- A copy of the IRB approved informed consent form.
- IRB member list and DHHS General Assurance Number (if IRB has an Assurance number).
- Signed Financial Disclosure Form for all personnel listed on the 1572.
- The signature page of this protocol signed and dated by the Principal Investigator.

In addition to the documents listed above, the study site will also retain the following items:

- Certifications and laboratory reference ranges for all local laboratories used for this study.
- All original informed consent forms with required signatures
- All IRB correspondence (*i.e.*, informed consent [including any approved revisions], protocol, AE, advertisements, newsletters)
- Copy of the Study Monitoring Log Sheet

- 
- Clinical and non-clinical supply shipment forms
  - Copies of all correspondence pertaining to the study (except budget issues) between the Sponsor or the CRO and the site
  - Copies of all SAEs reports submitted to the Sponsor its designee
  - Copies of all IND Safety Reports submitted to the site by the Sponsor its designee
  - Copies of approved package labeling
  - Study personnel signature log

All study-related records must be maintained for at least 2 years after a marketing application (NDA/BLA) is approved for the drug; or if an application is not approved for the drug, until at least 2 years after shipment and delivery of the drug for investigational use is discontinued and FDA/health authorities or regulatory agencies have been notified. The Sponsor will notify the principal Investigator when records are no longer needed. The Investigator will not discard any records without notifying the Sponsor. If the principal Investigator moves from the current investigational site, the Sponsor should be notified of the name of the person who will assume responsibility for maintenance of the records at the investigational site or the new address at which the records will be stored. The Investigator will notify the Sponsor as soon as possible in the event of accidental loss or destruction of any study documentation.

---

#### **16. INVESTIGATOR FINAL REPORT**

---

The Investigator shall provide the IRB and the Sponsor with an accurate final report within 3 months after completion, termination or discontinuation of the study. The final report may not precede retrieval of CRFs which have not been monitored.

---

#### **17. STUDY REPORT AND PUBLICATION**

---

The data resulting from this study will be the proprietary information of the Sponsor and may be made public after all data have been analyzed and the study results are available. None of the data resulting from this study will be allowed to be presented or published in any form, by the Investigator or any other person, without the prior written approval of the Sponsor. At the end of the study, a clinical study report will be written by the Sponsor or its designee.

---

---

**APPENDICES**

---

Appendix 1. Schedule of Evaluations and Visits & Laboratory Tests by Visit

**SCHEDULE OF EVALUATIONS AND VISITS**

Procedure	Screening / Baseline (-30 – 0 D)	1 st Injection Day 0		2 nd Injection Day 7 ± 1 D		3 rd Injection Day 14 ± 1 D		4 th Injection Day 21 ± 1 D		Day 30 ± 3 D	Day 60 ± 3 D	Day 90 ± 7 D	6 M ± 1 M	9 M ± 1 M	12, 18, 24 and 36 M	Withdrawal before 9M Visit
		Pre- dose	Post- dose	Pre- dose	Post- dose	Pre- dose	Post- dose	Pre- dose	Post- dose							
Baseline Evaluation																
Informed Consent	✓															
Medical History	✓															
Physical Exam	✓													✓		✓
Viral screening	✓															
EKG	✓													✓		✓
Urine Pregnancy test	✓															
Safety and Efficacy Parameters																
Concomitant Medications	✓	✓		✓		✓		✓		✓	✓	✓	✓	✓		✓
Vital Signs	✓	✓	✓	✓	✓	✓	✓	✓	✓	✓	✓	✓	✓	✓		✓
Serum Chemistry and Hematology	✓	✓								✓		✓		✓		✓
FVC	✓	✓ †								✓	✓	✓	✓	✓		
ALSFRS-R	✓	✓ †								✓	✓	✓	✓	✓		
Muscle strength (MRC Scale)		✓ †								✓	✓	✓	✓	✓		
Muscle circumference		✓ †									✓	✓	✓	✓		
Dynamometry		✓ †									✓	✓	✓	✓		
Serum HGF		✓		✓		✓		✓		✓	✓	✓				✓ 
Copies of VM202 in whole blood		✓	✓*	✓	✓*	✓	✓*	✓	✓*	✓	✓	✓				✓ 
Treatment																
Injection site reaction assessment			✓	✓	✓	✓	✓	✓	✓	✓	✓					✓ 
Adverse Events			✓	✓	✓	✓	✓	✓	✓	✓	✓	✓	✓	✓		✓
Phone call follow-up to assess survival															✓	

- † Can be conducted the day before injections  
 \* 2 hours after injection (± 1 hour)  
 1. If withdrawal occurred before Day 90 Visit  
 2. If withdrawal occurred before Day 60 Visit

**SCHEDULE OF LABORATORY EVALUATIONS**

Parameters	Screen	Day 0	Day 7, 14, 21	Day 30	Day 60	Day 90	6 Months	9 Months	Early Withdrawal
Serum HGF		✓ pre-injection	✓ pre-injection	✓	✓	✓			✓ (< Day 90)
VM202		✓ pre & post injection	✓ pre & post injection	✓	✓	✓			✓ (< Day 90)
HTLV, HIV-1, HIV-2	✓								
Hepatitis B and C †	✓								
Hematology									
Hematocrit	✓	✓		✓		✓		✓	✓
Hemoglobin	✓	✓		✓		✓		✓	✓
RBC	✓	✓		✓		✓		✓	✓
WBC with differential	✓	✓		✓		✓		✓	✓
Platelets	✓	✓		✓		✓		✓	✓
MCV	✓	✓		✓		✓		✓	✓
MCH	✓	✓		✓		✓		✓	✓
MCHC	✓	✓		✓		✓		✓	✓
Chemistry									
Albumin	✓	✓		✓		✓		✓	✓
Alkaline Phosphatase	✓	✓		✓		✓		✓	✓
ALT	✓	✓		✓		✓		✓	✓
AST	✓	✓		✓		✓		✓	✓
Bicarbonate	✓	✓		✓		✓		✓	✓
BUN	✓	✓		✓		✓		✓	✓
Calcium	✓	✓		✓		✓		✓	✓
Chloride	✓	✓		✓		✓		✓	✓
Creatinine	✓	✓		✓		✓		✓	✓
Glucose	✓	✓		✓		✓		✓	✓
Potassium	✓	✓		✓		✓		✓	✓
Sodium	✓	✓		✓		✓		✓	✓
Total Protein	✓	✓		✓		✓		✓	✓
Total Bilirubin	✓	✓		✓		✓		✓	✓

† Hepatitis B core antibody (HBcAb), antibody to Hepatitis B surface antigen (IgG and IgM; HBsAb), Hepatitis B surface antigen (HBsAg) and Hepatitis C antibodies (Anti-HCV)

---

Appendix 3. Medications Excluded from Use During the Study

**WASHOUT TABLE FOR COX-2 INHIBITORS & STEROIDS**

Drug	Example of Common Name(s)	Minimum Dose Allowed During Study	Washout Period
Cox-2 specific Inhibitors			
celecoxib	Celebrex	none	2 weeks
Non-steroidal Anti-inflammatory Drugs (NSAIDs: nonspecific inhibitors of both Cox-1 and Cox-2)			
acetylsalicylic acid	Aspirin Arthritis Foundation Safety Coated Aspirin, Bayer Aspirin, Bayer Children's Aspirin, Ecotrin	81 mg daily	2 weeks for doses over 81 mg daily
diclofenac	Voltaren Arthrotec, cambia, cataflam, flector, pennsaid, solaraze, zipsor	none	2 weeks
diflunisal	Dolobid	none	2 weeks
etodolac	Lodine	none	1 week
fenoprofen	Nalfon	none	1 week
flurbiprofen	Ansaid	none	1 week
ibuprofen	Motrin, Advil, caldolor, profen	none	1 week
idomethacin	Indocin	none	1 week
ketoprofen	Nexcede, Orudis	none	None for topical formulation, 1 week for all others
ketorolac	Sprix, acuvail, acular	none	1 week
mefenamic acid	Ponstel	none	1 week
meloxicam	Mobic	none	1 week
nabumetone	Relafen, Relifex and Gambaran	none	1 week
naproxen sodium	Aleve, Anaprox, Antalgin, Feminax Ultra, Flanax, Inza, Midol Extended Relief, Miranax, Naposin, Naprelan, Naprogesic, Naprosyn, Narocin, Proxen, Synflex, Xenobid	none	2 weeks
oxaprozin	Daypro	none	1 week
piroxicam	Feldene	none	1 week
sulindac	Clinoril	none	1 week
tolmetin	Tolectin	none	1 week
Corticosteroids (topical, injected, oral)	Prednisone, betamethasone, dexamethasone, cortisone, triamcinolone	none†	1 week

**Please note**, some of these medications are provided in combination with other drugs in new formulations (e.g. AGGRENOX® (aspirin/extended-release dipyridamole); Excedrin (acetaminophen; aspirin; caffeine))

† inhaled steroids for the treatment of respiratory disorders are allowed

---

Appendix 4. Test Article Administration

1. **Test article preparation**

**VM202** - VM202 is supplied in a sterile glass vial containing 2.5 mg of lyophilized study product. Before administration, it will be reconstituted with 5.0 mL of water for injection (WFI) for a final VM202 concentration of 0.5 mg / mL. Each reconstituted vial is only to be used for one subject.

ALS patients will receive injections both in the upper limbs and lower limbs. In order to reduce the injection burden on the ALS patient, injection of the upper limbs will be performed on separate visits from injection of the lower limbs. Depending on whether the upper or lower limbs will be injected first VM202 will be prepared as follows:

Table 5. Single dose preparation and delivery for Day 0, Day 7, Day 14, and Day 21 Visits

Treatment Arm	Number of Vials Reconstituted at each visit	Number of injections †	Total Volume to be Injected
Upper Limb Injections 13 mg VM202	██████████, ██████████ ██████████	■	██████████
██████████ ██████████	██████████ ██████████ ██████████	■	██████████

†Injection volume for each individual injection = 0.5 mL

2. **Test material administration** – Patients will receive injections of VM202 on Day 0, Day 7, Day 14 and Day 21. A fine needle (*e.g.* 27 gauge, 1”) suitable for IM injections will be used. Distribute injection sites evenly over each target muscle group, carefully avoiding fascia.

- Inject the entire amount of the drug per each injection in about 3-5 seconds. Immediately after completion of injection, lightly press the injection site with the finger head in order to prevent reflux. Do not massage the injection site.
- Subsequent administrations – Subsequent administrations should also be distributed evenly over each target muscle, and, as much as is possible, at different injection sites (if previously identified by an indelible marker). If marks made to identify previous injection sites are visible, every effort should be made to inject at alternate locations.

Sample injection sites for upper limb injections and lower limb injections are depicted in [Figure 4](#) and [Figure 5](#), respectively. The first eligible subject will begin with the lower limb injection series as assigned by the Sponsor or its designee and will be injected in accordance with the schedule outlined in [Table 6](#).

Table 6. Group 1 Injection Schedule

TARGET AREA	DOSE VM202 (mg) / TARGET MUSCLE, (NUMBER OF INJECTIONS / MUSCLE GROUP / SIDE (R/L))				TOTAL DOSE (TOTAL NUMBER OF INJECTIONS (R +L ))
	DAY 0	DAY 7	DAY 14	DAY 21	
[REDACTED]					
[REDACTED]		[REDACTED]		[REDACTED]	[REDACTED]
[REDACTED]		[REDACTED]		[REDACTED]	[REDACTED]
[REDACTED]		[REDACTED]		[REDACTED]	[REDACTED]
[REDACTED]		[REDACTED]		[REDACTED]	[REDACTED]
[REDACTED]		[REDACTED]		[REDACTED]	[REDACTED]
[REDACTED]		[REDACTED]		[REDACTED]	[REDACTED]
[REDACTED]		[REDACTED]		[REDACTED]	[REDACTED]
[REDACTED]		[REDACTED]		[REDACTED]	[REDACTED]
[REDACTED]		[REDACTED]		[REDACTED]	[REDACTED]
[REDACTED]		[REDACTED]		[REDACTED]	[REDACTED]
[REDACTED]		[REDACTED]		[REDACTED]	[REDACTED]
[REDACTED]	[REDACTED]		[REDACTED]		[REDACTED]
[REDACTED]	[REDACTED]		[REDACTED]		[REDACTED]
[REDACTED]	[REDACTED]		[REDACTED]		[REDACTED]
[REDACTED]	[REDACTED]	[REDACTED]	[REDACTED]	[REDACTED]	[REDACTED]
[REDACTED]	[REDACTED]	[REDACTED]	[REDACTED]	[REDACTED]	[REDACTED]

The next sequentially eligible patient will begin with injection of the upper limbs as assigned by the Sponsor or its designee (see [Table 7](#)). Subsequent eligible patients will be treated in an alternating fashion as assigned by the Sponsor or its designee, such that 9 patients will have initiated their VM202 injections in the lower limbs and 9 patients will have initiated their VM202 injections in the upper limbs. ***Please note: Regardless of injection order, all subjects will receive the same final dose of VM202 and the same number of injections per muscle group.***

Table 7. Group 2 Injection Schedule

TARGET AREA	DOSE VM202 (mg) / TARGET MUSCLE, (NUMBER OF INJECTIONS / MUSCLE GROUP / SIDE (R/L))				TOTAL DOSE (TOTAL NUMBER OF INJECTIONS (R + L))
	DAY 0	DAY 7	DAY 14	DAY 21	
[REDACTED]					
[REDACTED]	[REDACTED]		[REDACTED]		[REDACTED]
[REDACTED]	[REDACTED]		[REDACTED]		[REDACTED]
[REDACTED]					
[REDACTED]	[REDACTED]		[REDACTED]		[REDACTED]
[REDACTED]	[REDACTED]		[REDACTED]		[REDACTED]
[REDACTED]	[REDACTED]		[REDACTED]		[REDACTED]
[REDACTED]	[REDACTED]		[REDACTED]		[REDACTED]
[REDACTED]	[REDACTED]		[REDACTED]		[REDACTED]
[REDACTED]					
[REDACTED]		[REDACTED]		[REDACTED]	[REDACTED]
[REDACTED]		[REDACTED]		[REDACTED]	[REDACTED]
[REDACTED]		[REDACTED]		[REDACTED]	[REDACTED]
[REDACTED]	[REDACTED]	[REDACTED]	[REDACTED]	[REDACTED]	[REDACTED]
[REDACTED]	[REDACTED]	[REDACTED]	[REDACTED]	[REDACTED]	[REDACTED]

[Redacted text block]

us

.

[Redacted text block]

[Redacted text block]

---

Appendix 5. Revised Amyotrophic Lateral Sclerosis Functional Rating Scale (ALSFRS-R)

Bulbar	Fine Motor	Gross Motor	Breathing

1. Speech
 
 
4. Normal speech processes
 
3. Detectable speech disturbance
 
2. Intelligible with repeating
 
1. Speech combined with nonvocal communication
 
0. Loss of useful speech
 
 
2. Salivation
 
 
4. Normal
 
3. Slight but definite excess of saliva in mouth; may have nighttime drooling
 
2. Moderately excessive saliva; may have minimal drooling
 
1. Marked excess of saliva with some drooling
 
0. Marked drooling; requires constant tissue or handkerchief
 
 
3. Swallowing
 
 
4. Normal eating habits
 
3. Early eating problems-occasional choking
 
2. Dietary consistency changes
 
1. Needs supplemental tube feeding
 
0. NPO (exclusively parenteral or enteral feeding)
 
	
7. Turning in bed
 
 
4. Normal
 
3. Somewhat slow and clumsy, but no help needed
 
2. Can turn alone or adjust sheets, but with great difficulty
 
1. Can initiate, but not turn or adjust sheets alone
 
0. Helpless
 
 
8. Walking
 
 
4. Normal
 
3. Early ambulation difficulties
 
2. Walks with assistance
 
1. Non-ambulatory functional movement only
 
0. No purposeful leg movement
 
 
9. Climbing stairs
 
 
4. Normal
 
3. Slow
 
2. Mild unsteadiness or fatigue
 
1. Needs assistance
 
0. Cannot do
 
		

4. Handwriting
 
 
4. Normal
 
3. Slow or sloppy; all words are legible
 
2. Not all words are legible
 
1. Able to grip pen but unable to write
 
0. Unable to grip pen
 
 
5a. Cutting Food / Handling Utensils
 
 
4. Normal
 
3. Somewhat slow and clumsy, but no help needed
 
2. Can cut most foods, although clumsy and slow; some help needed
 
1. Food must be cut by someone, but can still feed slowly
 
0. Needs to be fed
 
 
5b. Cutting Food / Handling Utensils (Alt. for patients with Gastrostomy)
 
 
4. Normal
 
3. Clumsy but able to perform all manipulations independently
 
2. Some help needed with closures and fasteners
 
1. Provides minimal assistance to caregiver
 
0. Unable to perform any aspect of task
 
 
6. Dressing and hygiene
 
 
4. Normal function
 
3. Independent and complete self-care with effort or decreased efficiency
 
2. Intermittent assistance or substitute methods
 
1. Needs attendant for self-care
 
0. Total dependence
 
		
10. Dyspnea
 
 
4. None
 
3. Occurs when walking
 
2. Occurs with one or more of the following: eating, bathing, dressing (ADL)
 
1. Occurs at rest, difficulty breathing when either sitting or lying
 
0. Significant difficulty, considering using mechanical respiratory support
 
 
11. Orthopnea
 
 
4. None
 
3. Some difficulty sleeping at night due to shortness of breath. Does not routinely use more than two pillows
 
2. Needs extra pillow in order to sleep (more than two)
 
1. Can only sleep sitting up
 
0. Unable to sleep
 
 
12. Respiratory insufficiency
 
 
4. None
 
3. Intermittent use of BiPAP
 
2. Continuous use of BiPAP
 
1. Continuous use of BiPAP during the night and day
 
0. Invasive mechanical ventilation by intubation or tracheostomy
 
	

---

[figure not shown]

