### 3.3.2. EXCLUSION CRITERIA

---

Subjects *will not be eligible for the study* if any of the following criteria are present:

1. Neurological symptom(s) due to vitamin B12 deficiency;
2. Requires tracheotomy ventilation or noninvasive ventilation  $>$  16 hours / day;
3. Comorbidities such as Parkinson's disease, schizophrenia, renal failure, or any other severe complication that, in the Investigator's opinion, will compromise the safety of the patient or confound interpretation of the data collected in this study;
4. Other neuromuscular disease;
5. Inflammatory disorder of the blood vessels (inflammatory angiopathy, such as Buerger's disease);
6. Active infection;
7. Chronic inflammatory disease (e.g., Crohn's disease, rheumatoid arthritis);
8. Positive HIV or HTLV at Screening;
9. Active Hepatitis B or C as determined by Hepatitis B core antibody (HBcAb), antibody to Hepatitis B surface antigen (IgG and IgM; HBsAb), Hepatitis B surface antigen (HBsAg) and Hepatitis C antibodies (Anti-HCV) at Screening;
10. Subjects with known immunosuppression or currently receiving immunosuppressive drugs, chemotherapy or radiation therapy;
11. Stroke or myocardial infarction within last 3 months;
12. Patients with a recent history ( $<$  5 years) of malignant neoplasm except basal cell carcinoma or squamous cell carcinoma of the skin (if excised and no evidence of recurrence);

- 
13. Subjects requiring > 81 mg daily of acetylsalicylic acid; subjects may be enrolled if willing/able to switch to ≤ 81 mg daily of acetylsalicylic acid or to another medication;
  14. Subjects requiring regular COX-2 inhibitor drug(s) or non-specific COX-1/COX-2 inhibiting drugs, or high dose steroids (excepting inhaled steroids); subjects may be enrolled if willing/able to undergo medication wash-out prior to the first dosing and to refrain from taking these drugs for the duration of the study;
  15. Have used an investigational drug within 30 days of Screening;
  16. Pregnant or currently lactating;
  17. Major psychiatric disorder in past 6 months;
  18. Known drug or alcohol dependence or any other factors which will interfere with the study conduct or interpretation of the results or who in the opinion of the Investigator are not suitable to participate.
- 

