**4.2.7. REVISED AMYOTROPHIC LATERAL SCLEROSIS FUNCTIONAL RATING SCALE (ALSFRS-R)**

---

The revised Amyotrophic Lateral Sclerosis Functional Rating Scale (ALSFRS-R) is a validated rating scale for measuring the global function of patients with ALS. It

---

provides a health professional-generated estimate of the patient's degree of functional impairment, which can be evaluated serially to objectively assess any response to treatment or progression of disease. The ALSFRS-R includes twelve questions that ask the physician to rate his/her impression of the patient's level of functional impairment in performing one of twelve common tasks, *e.g.* climbing stairs. Each task is rated on a five-point scale from 0 = can't do, to 4 = normal ability. Individual item scores are summed to produce a reported score of between 0=worst and 48=best. The ALSFRS-R will be conducted at Screening, on Day 0 before the treatment (injection), on Day 30, Day 60, Day 90, at 6 months and 9 months. Details can be found in [Appendix 5](#).

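### In Appendix 5, item 12 of the ALSFRS-R has overlapping BiPAP levels and none for night-only use, so one pattern of use can take two scores, a difference of at most 1 point in 48

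*Combined protocol and SAP*

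**What the plan says.** Appendix 5 prints five levels for item 12. Level 4 is no respiratory insufficiency, and level 0 is invasive ventilation. The three levels between them concern BiPAP:

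- The mildest of the three is "3. Intermittent use of BiPAP", with no hours or time of day attached.
- The middle one is "2. Continuous use of BiPAP", again without any limit to night or day.
- The most severe is "1. Continuous use of BiPAP during the night and day", the only one that mentions a time of day.

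Neither *intermittent* nor *continuous* is defined by hours or time of day, in Appendix 5 or elsewhere, and no rule says which level wins when two apply.

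Section 4.2.7 gives the structure of the scale: "Each task is rated on a five-point scale from 0 = can't do, to 4 = normal ability". For the total, the same section states that "Individual item scores are summed to produce a reported score of between 0=worst and 48=best". It refers the rater to Appendix 5 for the details and schedules the scale at seven time points: Screening, Day 0, Day 30, Day 60, Day 90, 6 months and 9 months. Section 6.2 lists the ALSFRS-R among the secondary measures, and inclusion criterion 5 (section 3.3.1) requires a total of at least 30.

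On ventilation at entry, exclusion 2 in section 3.3.2 reads "Requires tracheotomy ventilation or noninvasive ventilation", the noninvasive part applying only above 16 hours a day.

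**The concern.** An ordinal item needs levels that exclude one another and together cover the patients who will be rated. As printed, item 12 fails on both counts within the BiPAP range. Anyone who meets level 1 also meets level 2, and a patient who uses BiPAP all night and never by day has no level of their own.

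Such patients are foreseeable. The ventilation criterion admits night-only users, section 1 gives respiratory failure as the commonest cause of death in ALS, and scored follow-up runs for 9 months. At stake is whether a change in the item between visits reflects the patient or the rater's reading. Appendix 7 asks for the same assessor, where possible, for muscle circumference. Section 4.2.7 has no such request for the ALSFRS-R. With a single arm there is also no untreated group in which the same scoring difference could offset it.

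**Working it through.** **1. The plan's own figure.** Twelve items with a maximum of 4 each give 12 × 4 = 48, which matches the range in section 4.2.7. The fault is in the wording of one item, not in the construction of the total.

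**2. Scores that the printed text allows.** Each pattern of use is set against every level whose wording admits it.

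| Pattern of use | Scores allowed by item 12 | Spread |
|---|---|---|
| No BiPAP | 4 | 0 |
| Intermittent BiPAP | 3 | 0 |
| All night, never by day | 3 or 2 | 1 |
| Continuous, night and day | 2 or 1 (literal reading) | 1 |
| Invasive ventilation | 0 | 0 |

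Two of the five patterns are ambiguous, each by 1 point. Relative to the full range, 1/48 = 2.1%.

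**3. Effect on change within a patient.** A patient who goes from no BiPAP to night-only use loses 4 − 3 = 1 point or 4 − 2 = 2 points, depending on the reading. A patient who then goes from night-only to night-and-day use can lose 3 − 1 = 2, 3 − 2 = 1, 2 − 1 = 1 or 2 − 2 = 0 points. In the last case a real worsening leaves no trace in this item.

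**4. Effect on the group mean.** If k of the 18 patients are scored 1 point differently in the same direction at a visit, the mean total moves by k/18. The documents give no rate of BiPAP use, so k is an assumption:

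- k = 1: 1/18 = 0.06
- k = 3: 3/18 = 0.17
- k = 6: 6/18 = 0.33

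These are upper figures for the number of BiPAP users. A clearly intermittent user scores 3 without doubt and does not count towards k.

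**5. Effect at entry.** Continuous night-and-day use should exceed 16 hours a day and so be excluded, which means the overlap of levels 2 and 1 should hardly arise at Screening. Entry also requires FVC of at least 60% of predicted. What remains is a night-only user whose total is 29 on one reading and 30 on the other.

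**The case against.** The strongest reply is that a trained rater will cope. A night-and-day user matches level 1 word for word, a rater on an ordered scale picks the most specific level that fits, and the contrast with level 1 points to level 2 as something less. This largely disposes of the overlap between levels 2 and 1 in practice. It does not settle night-only use, because *intermittent* fits that pattern too and nothing in the text rules it out.

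Second, the study is at one center. A consistent local reading would remove drift between visits and would cancel in change from baseline for a patient whose use does not change. That is fair, but it does not help a patient who starts BiPAP during follow-up, whose recorded drop still depends on which reading the center adopted.

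Third, the items of Appendix 5 appear out of order in the available text, so lost words cannot be excluded, and the CRF page is not in the documents. Item 12 shows no gap or redaction, and all five levels are legible. This is a reason to check the source form, not to drop the point.

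Fourth, the consequence is small. No hypothesis is tested, efficacy is descriptive only, and FVC is recorded separately at the same visits. All of that stands and limits the severity.

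A reader might also infer that the item is biased upwards and so understates decline. That would follow if night-only use properly scores 2. Appendix 5 does not say that it does, so the documents support ambiguity but no direction.

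**Conclusion.** Item 12 is wrong as written, and the severity is low. As printed it does not give one score per pattern of BiPAP use. Night-only use is the live ambiguity, and the overlap of levels 2 and 1 is a literal one that most raters would resolve.

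The size is bounded by 1 point per affected patient per visit and by k/18 on the group mean, the latter only if all k differ in the same direction. It falls mainly on follow-up scores of a descriptive secondary measure in a single-arm, open-label study. Safety and tolerability, the primary endpoint, are not affected.

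Two further inferences go beyond the documents. One is that eligibility is materially at risk: the 16-hour limit and the FVC criterion leave only a marginal case, and no frequency can be given for it. The other is that every BiPAP user would be mis-scored in the same way, which the text does not support. Being listed first among the secondary measures is also list order, not a declared ranking.

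**What to change.** Check item 12 of Appendix 5 against the published scale that section 4.2.7 cites (reference 52) and restore that wording. Confirm that levels 3, 2 and 1 then exclude one another and that each pattern of BiPAP use, night-only included, maps to one score. The level meanings should come from the source form, not from inference about what the present text intends. Use the corrected form and the matching CRF page at every visit from Screening, so that baseline and follow-up are scored by the same rule.

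The cost is a correction to one item in Appendix 5 and to one CRF page. No visit, procedure, patient or analysis is added, and the 0 to 48 range and the sample size of 18 stay as they are.
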